## **8.3 SCREENING ASSESSMENTS**

A screening (consultation) visit may occur as part of standard of care. If a participant is eligible for the study after review of key inclusion/exclusion criteria, additional screening visits will be scheduled while staff members are requesting insurance authorization to participate in a clinical trial.

The following will be reviewed at screening visit:

- Clinical history and physical exam (per standard of care)
- Informed consent obtained and documented

Toxicities which occur prior to the start of treatment will not be subject to analysis. Consent must be obtained before initiation of any clinical screening procedure that are performed solely for the purpose of determining eligibility for this research study. Evaluations performed as part of routine care before informed consent can be utilized as screening evaluations if done within the defined time period.

## **8.4 EARLY TERMINATION OR END OF STUDY VISIT**

Any participant who undergoes early termination will undergo end of study visits depending on their progress in the protocol. Participants who have not received BTX injection are not considered enrolled, will not require a follow up visit and will be treated per standard of care.

Participants who have received injection but not yet had surgery will have a follow-up visit within 30 days of intervention to evaluate for adverse events. Participants undergoing termination following pancreatectomy will have an end of study visit at the time of their regular post-op visit and will be cared for per the standard of care.

## **8.5 FOLLOW-UP**

Participants will be followed for 30 days following distal pancreas resection for efficacy. For safety, patients will be followed for 30 days following BTX injection if no surgery occurs or 30 days after surgery, whichever is longer. A follow-up visit will occur 14 days ( $\pm$  7 days)- following hospital discharge, consistent with standard of care practices. Additionally, all subjects will be contacted by phone by the NSQIP Surgical Clinical Reviewer ([name]) or other study team member approximately 30 days following operation to collect standard NSQIP other study datapoints. If a participant is diagnosed with any BTX-related adverse event (of any grade), additional follow-up phone calls will be performed monthly for three months following BTX injection to ensure resolution at the end of BTX duration of action.

Subjects not undergoing pancreatectomy and those undergoing pancreatectomy greater than 6 weeks from the date of BTX injection will not be evaluable for assessing efficacy of the study intervention but will be evaluable for assessing safety. The 6 weeks timepoint is chosen because the maximal efficacy of BTX may begin to wane following this timepoint. In patients undergoing BTX injection but not undergoing planned pancreatectomy (or experiencing a delay in pancreatectomy due to an AE from BTX), data on the reason(s) for delay or cancelled operation will be recorded.

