## 1.3 RISK/BENEFIT ASSESSMENT

### 1.3.1 KNOWN POTENTIAL RISKS

Botulinum toxin (onabotulinumtoxinA; Botox) has been used for decades with great efficacy in multiple conditions. BTX has an excellent safety profile, with one systemic review of 36 randomized controlled trials noting no serious adverse events, with focal weakness at/around the injection site being the only mild-moderate adverse event that occurred more often than controls, which is not a relevant risk for endoscopic injection. Post-marketing reports indicate that the effects of all botulinum toxin products may spread from the area of injection to produce symptoms consistent with botulinum toxin effects. These may include asthenia, generalized muscle weakness, diplopia, ptosis, dysphagia, dysphonia, dysarthria, urinary incontinence and breathing difficulties, depending on the site of injection. These symptoms have been reported hours to weeks after injection. Swallowing and breathing difficulties can be life threatening and there have been reports of death. The risk of symptoms is probably greatest in children treated for spasticity but symptoms can also occur in adults treated for spasticity and other conditions, particularly in those patients who have underlying conditions that would predispose them to these symptoms. In unapproved uses, including spasticity in children, and in approved indications, cases of spread of effect have been reported at doses comparable to those used to treat cervical dystonia and at lower doses.

In cases of endoscopic BTX injection, side-effects apart from asymptomatic serum lipase elevations or mild pancreatitis have not been previously reported when administered for Sphincter of Oddi dysfunction, post-cholecystectomy biliary pain, or for prevention of POPF.

Risks specific to endoscopy represent additional study-related risks, and include postinterventional pancreatitis defined by the Atlanta criteria which includes two of the following: 1) abdominal pain consistent with acute pancreatitis; 2) serum lipase  $> 3$  ULN; 3) characteristic imaging findings). Rare risks with the upper endoscopy procedure include cardiopulmonary compromise with procedural sedation, intraprocedural hemorrhage, and bowel perforation.

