### 8.1.5 ADVERSE EVENT EVALUATION

Toxicities and adverse experiences will be assessed using the [NCI CTCAE 5.0](#). Safety will be monitored by assessing physical examination, vital signs, body height (screening only) and weight as clinically indicated. Additionally, hematology, chemistry, coagulation, urinalysis, thyroid function, and pregnancy will be assessed as clinically indicated.

Adverse events will be monitored from the time the participant receives treatment on study. Participants will be instructed to report all AEs during the study and will be assessed for the occurrence of AEs throughout the study, including and up to 30 days. Due to the known excellent safety profile of botulinum toxin and FDA-approval for endoscopic injection for achalasia, AEs grade 1-2 will not be collected during the study. AEs Grade 3 or higher must be recorded on the source documents and eCRFs regardless of the assumption of a causal relationship with the study drug.

Abnormal laboratory values will only be recorded as an AE if determined to be clinically significant by the investigator.

For details on AE collection and reporting, refer to Section 10.

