#### 10.2.4 SEVERITY OF EVENT

Due to the known safety profile of botulinum toxin and FDA-approval for endoscopic injection for achalasia, AEs grade 1-2 will not be collected during the study. For serious AEs (Grade 3 or higher), the Investigator will grade its severity using, when applicable, the current version of the

CTCAE v5.0. In the event of an AE for which no grading scale exists, the Investigator will classify the AE as defined below:

---

- Grade 1:** Mild; asymptomatic or mild symptoms; clinical or diagnostic observations only; intervention not indicated.
- Grade 2:** Moderate; minimal, local or noninvasive intervention indicated; limiting age-appropriate instrumental ADL
- Grade 3:** Severe or medically significant but not immediately life-threatening; hospitalization or prolongation of hospitalization indicated; disabling; limiting self-care ADL.
- Grade 4:** Life-threatening consequences; urgent intervention indicated.
- Grade 5:** Death related to AE.

---

*Note: a semi-colon indicates 'or' within the description of the grade.*

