## 10.5 TIME PERIOD AND FREQUENCY FOR EVENT ASSESSMENT AND FOLLOW-UP

The occurrence of an UP, AE or SAE may come to the attention of study personnel during study visits and interviews of a study participant presenting for medical care, upon review by a study monitor, or during an audit. All AEs grade 3 or higher but not meeting the criteria for SAEs will be captured on the appropriate CRF. AEs of grade 1 and 2 will not be captured due to the well-characterized side effect profile of BTX for other indications, including endoscopic BTX injection which is FDA approved. Information to be collected includes event description, time of onset, clinician's assessment of severity, seriousness, expectedness, relationship to study product (assessed only by those with the training and authority to make a diagnosis), and date of resolution/stabilization of the event. All AEs grade 3 or higher occurring while on study must be documented appropriately regardless of relationship. All AEs will be followed to adequate resolution.

Any medical condition that is present at the time that the participant is screened will be considered as baseline and not reported as an AE. However, if the study participant's condition deteriorates at any time during the study, it will be recorded as an AE after treatment with study intervention begins.

Changes in the severity of an AE will be documented to allow an assessment of the duration of the event at each level of severity to be performed. AEs characterized as intermittent require documentation of onset and duration of each episode.

At each study visit, the Investigator will inquire about the occurrence of AE/SAEs since the last visit. Events will be followed for outcome information until resolution or stabilization.

The Investigator will record all reportable events with start dates occurring after treatment with study intervention begins for 30 days (for AEs grade 3 or higher) after the intervention is performed or 30 days after date of surgery, whichever is longer. AEs will be evaluated using the current version of the [CTCAE v5.0](#). At each study visit, the investigator will inquire about the occurrence of AE/SAEs since the last visit. Events will be followed for outcome information until resolution or stabilization. Any SAE that occurs after treatment with alternative therapy

will be reported only if the Investigator or current treating physician has assessed the SAE as related to the study treatment.

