#### 11.4.4 SAFETY ANALYSES

Adverse events will be tabulated by the Medical Dictionary for Regulatory Activities (MedDRA Version 21.1) preferred term and system organ class. The severity of the AE will be assessed by National Cancer Institute (NCI) Common Terminology Criteria for Adverse Events (CTCAE) version 5.0. Using the safety analysis set, descriptive statistics will be used to summarize all on-study AEs, grade 3-4 AEs, treatment-related AEs, grade 3-4 treatment-related AEs, SAEs, treatment-related SAEs, and AEs leading to study therapy discontinuation. Grade 3-4 laboratory abnormalities will be summarized using worst grade NCI CTCAE v5.0 criteria.

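### Grade 1-2 AEs are not collected, yet 8.5 follows BTX-related AEs of any grade and 11.4.4 tabulates all AEs, so related low-grade events could be followed without a required record

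*Combined protocol and SAP*

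**What the plan says.** The collection rule appears three times in the combined protocol and SAP.

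- Section 8.1.5: "AEs grade 1-2 will not be collected during the study".
- Section 10.2.4: "AEs grade 1-2 will not be collected during the study. For serious AEs (Grade 3 or higher", after which severity grading is described for that group.
- Section 10.5, with its reason: "AEs of grade 1 and 2 will not be captured due to the well-characterized side effect profile of BTX for other indications".

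The positive duty is in 8.1.5: "AEs Grade 3 or higher must be recorded on the source documents and eCRFs regardless of the assumption of a causal relationship".

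Section 8.5 works to a different threshold: "If a participant is diagnosed with any BTX-related adverse event (of any grade". In that case the participant is phoned each month for three months after injection, to confirm that the event has resolved.

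Section 11.4.4 then says that "descriptive statistics will be used to summarize all on-study AEs, grade 3-4 AEs", and lists treatment-related AEs separately from grade 3-4 treatment-related AEs. On the injection itself, 1.3.1 states that "side-effects apart from asymptomatic serum lipase elevations or mild pancreatitis have not been previously reported".

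**The concern.** Section 8.5 can only operate if someone diagnoses a BTX-related event, attributes it to BTX and follows it to resolution. For a grade 1-2 event, the collection sections do not require any of this to be written down as an AE. Section 11.4.4 is drafted as though lower-grade data will exist.

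Safety is a secondary objective (2.2). The reasons given for the exclusion are experience in other indications and the achalasia approval, not injection of the sphincter of Oddi before distal pancreatectomy. Section 1.1 says this use has not been studied in an American population. A reader of the final safety tables who saw no mild related events in a row labelled as all AEs could not tell whether none occurred or none were collected.

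**Working it through.** No figure in the plan is at issue, so the check sets the sections side by side.

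**1. Trigger against record.** The 8.5 trigger is BTX-related, any grade. The duty to record in 8.1.5 and 10.5 is grade 3 or higher, any cause. The difference between the two is the set of BTX-related grade 1-2 events.

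**2. Which of those are captured by another route.**

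| Event | Required record? | Basis |
|---|---|---|
| Pancreatitis with hospitalization | Yes, no grade condition | SAE in 10.2.2; endpoint in 2.2; run-in rule in 11.4.5 |
| Procedure-related complication that delays surgery | Yes, no grade condition | SAE in 10.2.2; delay counted in 2.2 |
| BTX-related grade 1-2 event with neither, e.g. mild pancreatitis managed at home | No AE record required | 8.1.5, 10.2.4, 10.5 |
| Asymptomatic lipase elevation | Mostly not detected | No lipase test is named in the study schematic; laboratory values count only if judged clinically significant (8.1.5) |
| Unrelated grade 1-2 event | No | Deliberate exclusion, consistent with 8.5 |

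The gap is the third row. The fourth is mainly a consequence of the testing plan, not of the grade rule.

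**3. The 11.4.4 rows.** With collection limited to grade 3 or higher, the row for all AEs can differ from the grade 3-4 row only by grade 5 events and by any lower-graded event that enters because it meets an SAE criterion. The same holds for the treatment-related pair. The labels promise more than the data can hold.

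**4. The recording window.** Section 10.5 records events starting up to 30 days after injection or 30 days after surgery, whichever is longer. Counting days from injection:

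- Surgery at day 7 to 14: the window closes at 7 + 30 = 37 to 14 + 30 = 44.
- Surgery at the six-week limit in 8.5: 42 + 30 = 72.
- Three months of calls: about 3 x 30 = 90.

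The calls therefore outlast the window by about 90 - 44 = 46 to 90 - 37 = 53 days on the planned schedule, and by about 90 - 72 = 18 days at the six-week limit. Section 10.5 does follow events until they resolve or stabilize, so an event already on the eCRF can be closed out later. An event never entered cannot, and a new one first reported at a late call falls outside the window.

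**5. Size.** The documents give no rate of mild related events. Purely as an assumption, 5% to 10% of 55 injected participants would be 55 x 0.05 = 2.75 to 55 x 0.10 = 5.5, or about 3 to 6 people. This indicates the data-entry load. It does not estimate what is lost, because some such events could be captured through hospitalization or delay.

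**The case against.** The exclusion is stated three times with a reason, so it is a choice and not an oversight. Section 8.5 is conditional and serves the participant's follow-up; it does not itself order data collection, and following someone clinically without an entry in an AE table is possible. Other provisions may leave traces: 8.1.4.1 sends significant new findings after consent to the AE eCRF without a grade limit, 8.6 puts study-related assessments from unscheduled visits in the CRF, and 7.4 requires medications to be listed. The 11.4.4 wording can be read as all AEs that were collected, and deaths stay visible as SAEs. Limiting 8.5 and 11.4.4 to grade 3 or higher would also remove the mismatch.

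Much of this stands. Excluding unrelated low-grade events around major surgery is reasonable. The grade 3-4 label is a wording point. It would be wrong to say that no trace of a mild event could exist. What remains is that none of these provisions guarantees an AE record of the event and its resolution, and that 8.1.4.1 itself conflicts with 8.1.5.

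A reader might infer from 1.3.1 that the only side effects previously reported for this injection cannot be reported at all, or that the safety objective fails. The documents do not support that. Pancreatitis requiring hospitalization and procedure-related complications delaying surgery are captured whatever their grade. The secondary endpoint is a rate of serious events, including grade 3 or higher AEs attributable to BTX, and needs no grade 1-2 data. A reader might also take 8.5 to cover endoscopy-related events; it names only BTX-related ones.

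**Conclusion.** The inconsistency is real but limited. Sections 8.1.5, 10.2.4 and 10.5 cannot all be applied alongside 8.5 and 11.4.4 as worded. The loss is confined to BTX-related grade 1-2 events with neither hospitalization nor surgical delay, and to two table rows whose labels would mislead. The primary endpoint and the secondary SAE rate are untouched. Asymptomatic lipase elevations would largely be missed under either rule. The conclusion rests on the text alone; the number of events affected is unknown. The change is worth making because 8.5 already has staff diagnose, attribute and follow these events, so only the recording step is missing.

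**What to change.** 1. In 8.1.5, 10.2.4 and 10.5, require any grade 1-2 event judged BTX-related to be recorded on the AE eCRF, with its resolution as found at the 8.5 calls. Keep the exclusion for unrelated grade 1-2 events.
2. In 10.5, extend the recording window for BTX-related events to cover the period of those calls.
3. In 11.4.4, write *all collected AEs* and *grade 3-5*, and state that unrelated grade 1-2 events were not collected.
4. Align 8.1.4.1 with the same rule.

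Recording endoscopy-related grade 1-2 events as well would be an optional extension beyond 8.5. The cost is a few eCRF lines and data entry for a small number of related events. No visit, test or call is added.

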## **8.6 UNSCHEDULED VISITS**

Unscheduled study visits may occur at any time if medically warranted. Any assessments performed (e.g., laboratory or clinical assessments) at those visits that, in the opinion of the investigator, are deemed related to this study should be recorded in the CRF.

## 8.7 SCHEDULE OF EVENTS

Visit Days ( $\pm$ 7 Days)	Screening	Days*		Follow-up
	Days -1 to -28	1	Days 2-14 (one pre-operative medicine visit within this time frame)	
BTX Administration		X		Day of Surgery 0-30 Days Post-Surgery or Two Weeks Post-Discharge (if LOS >30 Days)**
Informed consent	X			
Inclusion/exclusion criteria	X			
Medical history	X			
Prior/concomitant medications	X	X		
Standard of Care Pre-Intervention Labs	X		X	
Height and weight	X	X		
Comprehensive physical examination	X			
Physical Examination	X	X	X	
Vital signs	X	X	X	
Efficacy Assessments				
AE assessment			X	
Follow-up data collection				
Amylase Measurement(s)				
Phone call for efficacy evaluation				

\*Length dependent on scheduling of surgery, but will not be shorter than 7 days  
 \*\* Follow-up event can occur two-weeks post discharge (if LOS > 30) but collects information related to first 30 days post-surgery

Please note that patients will undergo an in-person pre-operative medicine exam prior to distal pancreatectomy/RAMPS per standard of care. Additionally, at the clinician's discretion patients may undergo pre-procedure medicine evaluation appointment prior to upper endoscopy and BTX injection.

## 9. EFFICACY MEASURES

Therapeutic efficacy will be evaluated in this study by the presence of any POPF, clinically relevant POPF, postoperative length of stay, and major postoperative complications.

### 9.1 DEFINITION OF EFFICACY MEASURES

#### 9.1.1 ANY POPF

Amylase level  $>3x$  the upper limit of normal from a fluid specimen obtained on postoperative day 3 or later, from a surgical drain or intra-abdominal fluid collection.

#### 9.1.2 CLINICALLY RELEVANT POPF (GRADE B AND C POPF)

1. Amylase level  $>3x$  the upper limit of normal from a fluid specimen obtained on postoperative day 3 or later from postoperatively placed percutaneous or endoscopic drain of an intra-abdominal fluid collection (Grade B POPF).

OR

2. Amylase level  $>3x$  the upper limit of normal from a fluid specimen obtained on postoperative day 3 or later from a surgical drain, postoperatively placed percutaneous or endoscopic drain of an intra-abdominal fluid collection, combined with organ failure clearly attributable to the POPF (Grade C POPF).

Major postoperative complications: Any postoperative complication filling criteria for Clavien-Dindo grade III or higher.

Length of stay: Number of midnights in-hospital following distal pancreas resection

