### 1.1.1 OVERVIEW OF STUDY TERMS

**Distal Pancreatectomy.** Distal pancreatectomy (removal of the distal pancreas +/- spleen) is indicated in nonmetastatic PDAC, and other neoplasms when disease is localized in the pancreatic tail, as well as in certain patients with chronic pancreatitis. A variant technique of distal pancreatectomy, termed radical antegrade modular pancreateosplenectomy (RAMPS) is often used specifically for malignancies of the pancreas. Pancreatic surgery is technically difficult and highly morbid, with POPF being the most feared complication by clinicians and patients.

**Postoperative Pancreatic Fistula (POPF).** POPF results when digestive enzymes normally secreted by the pancreas leak into the abdominal cavity following an operation, leading to a wide range of inflammatory and auto-digestive complications. POPF is defined by the International Study Group of Pancreatic Fistula (ISGPF) as an amylase level obtained from drainage fluid or abscess of greater than three times the upper limit of normal, starting from the third postoperative day (POD3). POPF is further classified by the ISGPF into biochemical leaks (asymptomatic elevations in amylase from surgical drain fluid that do not require additional treatment), Grade B POPF (requiring percutaneous or endoscopic drainage), or Grade C POPF (resulting in organ failure); together, Grades B/C constitute clinically-relevant POPF (crPOPF). Rates of POPF following distal pancreatectomy range from 20-50% with an average of 30%, with a 10-year average of at OHSU of 30.9% for all POPF and 11.3% for crPOPF.

[figure not shown]
**Sphincter of Oddi.** The Sphincter of Oddi is a smooth muscle valve located at the Ampulla of Vater that regulates the flow of bile and pancreatic secretions into the duodenum. Following distal pancreatectomy, the resting muscle tone of the Sphincter of Oddi may act as a dam, causing the “path of least resistance” for pancreatic secretions to be the cut edge of the pancreas, resulting in POPF as secretions exit into the abdominal cavity and cause an intense autodigestive and inflammatory reaction.

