### **8.2.5 AMYLASE ASSAY**

Amylase levels will be drawn from all surgical drains, when present, on postoperative day 3 or 4, per standard of care prior following pancreas resections. In patients undergoing percutaneous drainage of a postoperative intra-abdominal fluid collection, amylase levels on the drained fluid will be drawn to evaluate for crPOPF. An amylase level  $>3$  times the upper limit of normal from a surgical drain is sufficient for diagnosis of POPF, while an amylase level  $>3$  times the upper limit of normal from a percutaneous drain is sufficient for a diagnosis of crPOPF.

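### Sections 1.1.1 and 9.1.2(1) classify the same patient differently on the primary endpoint: a POPF proven on the surgical drain that then requires a new drain, whose fluid tests at or below 3x ULN

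*Combined protocol and SAP*

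**What the plan says.** Section 9.1.2 is the operative definition of the primary endpoint. Item 1 (Grade B) requires amylase above 3x ULN in a specimen obtained "on postoperative day 3 or later from postoperatively placed percutaneous or endoscopic drain of an intra-abdominal fluid collection (Grade B POPF". Item 2 (Grade C) also accepts a surgical-drain specimen, but only "combined with organ failure clearly attributable to the POPF (Grade C POPF".

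Section 1.1.1 builds the same grades in two steps. A POPF is "an amylase level obtained from drainage fluid or abscess of greater than three times the upper limit of normal", from the third postoperative day. It is then graded by its consequence: "Grade B POPF (requiring percutaneous or endoscopic drainage), or Grade C POPF (resulting in organ failure". The lowest category is "biochemical leaks (asymptomatic elevations in amylase from surgical drain fluid that do not require additional treatment". Nothing in 1.1.1 requires the new drain's own fluid to be positive.

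Section 9.1.1 counts any POPF on a positive specimen "from a surgical drain or intra-abdominal fluid collection". Section 8.2.5 says that a raised amylase "from a surgical drain is sufficient for diagnosis of POPF", and that the same result from a percutaneous drain is sufficient for crPOPF. Section 2.1 refers the primary endpoint to the ISGPF criteria, and the protocol's only summary of their grading is the one in 1.1.1.

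**The concern.** The two sections part company on one kind of record: surgical-drain amylase above 3x ULN on day 3 or later, a POPF that then requires percutaneous or endoscopic drainage, and new-drain fluid that was tested and found at or below 3x ULN. Section 1.1.1 makes this Grade B and hence a primary-endpoint event. Section 9.1.2(1) does not.

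The record is specific. It is not a missing amylase, an untested drain or a re-operation.

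Two things are at stake. First, the decision rules have no slack. Stage 1 continues on 1 crPOPF in 25 and stops on 2; the final result is promising on 2 in 50 and not on 3. The trial is open-label and single-arm. Section 13.1.2.1 lets people other than the NSQIP reviewer read charts for the interim, and has the study team resolve discrepancies without stating a rule for this case. Two careful readers could each cite a protocol section and disagree.

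Second, the trial count is compared with a fixed historical rate. If that rate was built on the broader definition, a narrower trial definition lowers the count on one side only.

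**Working it through.** **1. Apply both definitions to three records.**

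| Record | Section 1.1.1 | Section 9.1.2 |
|---|---|---|
| (a) No surgical drain; percutaneous drain placed, fluid >3x ULN | Grade B | Grade B (item 1) |
| (b) Surgical drain >3x ULN; POPF requires a new drain, fluid >3x ULN | Grade B | Grade B (item 1) |
| (c) Surgical drain >3x ULN; POPF requires a new drain, fluid tested and ≤3x ULN | Grade B | Any POPF only, unless organ failure attributable to the POPF (item 2) |

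Only (c) differs. Section 8.2.5 does not settle it. It calls a positive percutaneous-drain result sufficient, whereas 9.1.2(1) makes a positive new-drain result necessary and offers no other route to Grade B.

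**2. Reproduce the plan's design figures.** Inputs from Sections 11.2 and 11.4.5: null 0.112, alternative 0.02, 25 patients per stage, stop on 2 or more of the first 25, promising on 2 or fewer of 50. With X1 and X2 the counts in the two stages, each Bin(25, p):

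P(promising | p) = P(X1=0) × P(X2≤2) + P(X1=1) × P(X2≤1)

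- p = 0.02: 0.6035 × 0.9868 + 0.3079 × 0.9114 = 0.876 (plan: power 0.876).
- p = 0.112: P(X1≤1) = 0.0513 + 0.1618 = 0.213, so early termination is 0.787 (plan: 0.787). Expected size is 25 + 25 × 0.2132 = 30.33 (plan: 30.33).
- p = 0.112: 0.0513 × 0.4581 + 0.1618 × 0.2132 = 0.058. This is the baseline below. That it exceeds the stated one-sided 0.05 is a separate matter.

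**3. Size of the effect, if the historical rate used the broader definition.** The documents give no frequency for record (c). Let s be the assumed share of crPOPFs under 1.1.1 that are type (c) and are not rescued by item 2. The countable rate for an ineffective injection is then 0.112 × (1 − s).

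| Assumed s | Countable rate | Pass stage 1 | Declared promising | At least one type (c) in 50: 1 − (1 − 0.112s)^50 |
|---|---|---|---|---|
| 0 | 0.1120 | 0.213 | 0.058 | 0 |
| 5% | 0.1064 | 0.239 | 0.072 | 0.245 |
| 10% | 0.1008 | 0.267 | 0.090 | 0.431 |
| 20% | 0.0896 | 0.331 | 0.136 | 0.678 |

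For s = 10%: 0.0702 × 0.5317 + 0.1968 × 0.2670 = 0.090.

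**4. In patients.** At the null, 50 × 0.112 = 5.6 crPOPFs are expected in 50. A 5% share is 5.6 × 0.05 = 0.28 patients. At the 2% alternative with a 10% share, the chance of any type (c) patient in 50 is 1 − (1 − 0.002)^50 = 0.095.

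**The case against.** The best defence is that item 1 is deliberate. Section 8.2.5 draws the same line as 9.1.2: surgical-drain fluid establishes POPF, and percutaneous-drain fluid is tested to look for crPOPF. A low amylase in the drained collection may mean that the collection had another cause, and item 1 can be read as the plan's attribution test. Section 1.1.1 is background, and it speaks of a POPF that requires drainage, not of any drainage in a patient with a POPF.

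Much of this stands. A reader might infer that item 1 is a wording slip because item 2 accepts surgical-drain fluid. The documents do not show that, since item 2 carries its own attribution clause. Nor does 1.1.1 make every positive surgical drain followed by a drainage procedure Grade B. The conflict is confined to patients whose POPF is what required the drainage. For them, 1.1.1 counts the event and 9.1.2(1) has no place for it.

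A reader might also infer that the rule certainly biases the trial towards a promising result, because the OHSU rate of 11.3% is quoted straight after the broader definition. Proximity is the only support. Sections 11.4.3 and 13.1.2.1 indicate that the historical cohort and the trial outcomes both draw on NSQIP pancreatectomy data, so a common definition is equally possible. With one, there is no differential bias and the raised probabilities do not apply.

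Finally, type (c) patients do not vanish from the report. Any POPF, percutaneous drainage and Clavien-Dindo III or greater are all endpoints. None of these enters the Simon decision.

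**Conclusion.** The point holds as a contradiction in the primary-endpoint definition. The same patient is a crPOPF under 1.1.1 and not under 9.1.2(1), with item 2 as the only exception, and no other section resolves it. It should be settled before any such case has to be adjudicated in an open-label trial where a single event decides each stage.

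The frequency is unknown and probably low, because three conditions must coincide: a positive surgical drain, a later drain required by the POPF, and a tested, low result. The direction of any bias is conditional. If the historical 11.2/11.3% was counted under the broader definition, the chance of declaring an ineffective injection promising rises from 0.058 to between 0.072 and 0.136 over assumed shares of 5% to 20%. Those shares are illustrations, not estimates. If both rates were counted under one definition, the effect on the comparison is nil and only the inconsistency remains.

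**What to change.** Reconcile the sections by rewording 9.1.2(1) as a classification rule, for example: *Grade B POPF: amylase above 3x ULN in any fluid sampled on day 3 after surgery or later, whether from the surgical drain or from a percutaneous or endoscopic drain placed after surgery, together with percutaneous or endoscopic drainage, after surgery, of an intra-abdominal collection attributable to the POPF.* This follows 1.1.1 and uses the specimen sources that item 2 already allows. The attribution clause matters: without it, an unrelated collection drained in a patient with a positive surgical drain would count.

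State in Section 11.2 the definition under which the historical 11.2/11.3% was counted. Report the crPOPF count under the present new-drain-only wording as a sensitivity analysis.

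The cost is one reworded sentence, one added statement and one extra count, with no new test or visit. The rewording brings an attribution judgement, of the kind item 2 already needs, and the observed crPOPF rate may be slightly higher. Recounting historical events under the new rule would be additional work: the chart review in Section 11.4.3 is planned for predictive variables, not for re-adjudicating events.
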